## 2.3 Interventions

The package of locally tailored adolescent nutrition interventions will include in-school education about nutrition and healthy food choices, mentoring and peer group activities related to nutrition, and parent education on adolescent nutrition during school and community meetings. Intervention components are presented in **Table 2**.

Table 2. Description of interventions for treatment and control primary schools

CORE INTERVENTIONS	INTERVENTION PRIMARY SCHOOLS	CONTROL PRIMARY SCHOOLS
At school:		

 
Classroom education about healthy diet and nutrition
 
	Classroom lessons related to nutrition, dietary diversity, healthy food choices and hand washing	Standard health education

 
Flag events or assemblies about healthy diet and nutrition
 
	Flag events or school assemblies led by principals to provide messages on nutrition, dietary diversity, healthy food choices and hand washing	Standard flag ceremonies or assemblies

 
Peer group mentoring on healthy diets and nutrition
 
	Selected adolescent girls are mentored by science teachers as peer mentors and hold weekly group discussions with other girls to discuss nutrition, dietary diversity, healthy food choices and handwashing	None

 
BMI measurement and counseling
 
	Trained science teachers take anthropometric measurements of adolescent girls to calculate BMI and provide nutrition counseling	None
Parent-teacher meetings	Parent-teacher meetings to inform and encourage parents about adolescent nutrition, dietary diversity, healthy snacks, and handwashing	Parent-teacher associations focused on school performance and management
Home visits by health workers	Home visits by HEWs and/or community volunteers to discuss with parents about adolescent nutrition, dietary diversity, i healthy food choices, and handwashing	Home visits for routine health services
Community gatherings to discuss adolescent nutrition	Community gatherings by HEWs and meetings with religious leaders to discuss with parents about adolescent nutrition, dietary diversity, healthy food choices, and handwashing	None
Training for school staff and other actors	Workshop on the adolescent nutrition interventions above for school principals, science teachers, HEWs, supervisors, and woreda officers	Standard education training

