## 2.6 Sample Size

The primary study sample is adolescent girls enrolled in primary school and aged 10-14 years (grades 4-8). The sample size was estimated based on current prevalence of the primary outcome, the expected change after intervention, power to detect those differences (80%), and level of significance ( $\alpha=0.05$ ). As the intervention was randomized at the cluster level (54 clusters) rather than the individual level, cluster effect was considered for sample size calculation.

We used the number of food groups from the A&T Phase 1 endline survey for SNNPR (mean: 3.26, SD: 1.40, categorized as 9 food groups; Arimond et al., 2010), assuming an intra-cluster correlation (ICC) of 0.18. We calculated that a minimum sample of 189 girls per group will be able to detect a minimum of 0.6 food group consumption increase. The sample size at endline will be rounded to 270 girls per group so that 10 girls per school (2 per grade) will be sampled. Based on baseline data, we observed a mean of 3.69, SD: 1.56, categorized as 10 food groups. Assuming an ICC of 0.015, we estimated that this sample size will detect a minimum difference of 0.5 food groups.

School principals, science teachers and HEWs responsible for providing nutrition education or facilitating other related activities/interventions will also be included in both baseline and endline surveys.

At baseline, a light data collection at schools and subsamples of adolescent girls and their parents will be conducted to assess comparability between study arms. At endline, the full samples of adolescent girls and their parents will be surveyed (including those who participated at baseline).

Thus, the overall study samples are presented in **Table 3**.

Table 3. Sample sizes

	Baseline 2019		Endline 2021	
	Intervention	Control	Intervention	Control
Adolescent girls	81	81	270	270
Parents of adolescents	81	81	270	270
Principals (1 per school)	27	27	27	27

Science teachers (1 per school)	27	27	27	27
HEWs (1 per school)	27	27	27	27
Total	243	243	621	621

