#### 4.1.5 Parent questionnaire

Interviews with parents of adolescent girls will be conducted at baseline and endline and gather information on school involvement, exposure to nutrition information, dietary diversity, health and nutrition knowledge, food security, home food environment, social desirability, gender and marriage beliefs and decision-making power, dwelling and assets.

Table 9. Description of modules in the adolescent girls' parents' questionnaire

Module	Topic	Description	Respondent
1	Identification	School and respondent type	Enumerator
2	Household roster	Information on composition of the household, including designation of the head of household, a list of all household members, their ages and sex, and their relationship to the adolescent girl, and the highest educational level attained and activity/employment in the past month of all household members at least 15 years of age	Parent
3	School involvement	School fees, and participation in parent-teacher association, school management committee and teacher meetings	Parent
4	Exposure to nutrition information	Exposure to adolescent nutrition and/or WASH information, and exposure to media and food/drink advertisements	Parent
5	Dietary diversity	Dietary diversity of the adolescent and household in the past 24 hours	Parent
6	Home food environment	Availability of foods at home	Parent
7	Health and nutrition knowledge	General knowledge of health and nutrition, including WASH and	Parent

		importance of various macro and micronutrients	
8	Parent-adolescent interactions	Relationship and interactions with adolescent, monitoring of food and eating habits, adolescent weight and body image	Parent
9	Social desirability	Desire for social approval	Parent
10	Gender, marriage beliefs and decision-making power	Opinions about girls' and boys' education, marriage and household roles, and decision-making power in the household	Parent
11	Food security	Prevalence of household hunger using the FANTA household food insecurity access scale (HFIAS)	Parent
12	Dwelling	House construction (materials used for floor, walls, and roof), availability of water and electricity, sources of fuel/energy for cooking, WASH facilities	Parent
13	Assets	Ownership of durable household goods (in working condition), including tools for agricultural production	Parent

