## 1.2 Impact evaluation study design

The impact evaluation of A&T's interventions used a cluster-randomized design with repeated cross-sectional surveys at baseline and endline. We applied stratified random allocation to 54 primary schools within 7 districts (*woredas*) across two regions (SNNP and Somali), which were assigned to either the A&T intervention schools (27 schools) or control schools (27 schools). A small baseline survey was conducted in October-November 2019, and the endline survey was conducted in March-May 2021 in the same 54 schools, thereby creating panel data at the school level (not at individual level). Program implementation duration was approximately 4 months (1 school semester); implementation faced major disruptions due to the COVID-19 pandemic throughout most of 2020, with state lockdown/restrictions and school closures, until schools reopened in October 2020.

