### 3.3 Impact estimates

The main analysis of impacts will be performed using intent-to-treat (ITT) specifications, wherein all study participants in the originally assigned program group at baseline are included in the statistical analysis and analyzed according to their program group, regardless of whether they received interventions or not. Respondents who refused or withdrew consent or those who are ineligible according to study protocol are excluded from ITT analysis.

The main impacts of the interventions will be estimated for: (1) dietary diversity score, (2) consumption of unhealthy foods/junk foods, and (3) meal frequency. Secondarily, impact will be estimated for exposure to the core interventions: classroom lessons about adolescent nutrition and healthy diets, flag ceremonies/assemblies to remind about key healthy eating messages, adolescent girls club/student peer mentoring on adolescent nutrition, and parent-teacher meetings to educate parents about adolescent nutrition and healthy diets. All impact indicators will be assessed among adolescent girls, except for the exposure to parent-teacher meetings which will be assessed from parents.

Given that the main impact indicators with full sample sizes were collected at endline only, linear regression models will be used to test the means of the outcome for estimates of group differences (intervention vs. control) at endline, with standard errors clustered at the school level. In the adjusted models, we will control for covariates such as adolescent girl age and other variables that differed between study arms. Robustness tests will be conducted using difference-in-differences analysis where outcome variables exist at baseline.

Table 6. Dummy table for impact estimates

Indicator	Baseline		Endline		Unadjusted impact est. 	Adjusted impact est. 
	A&T (N=)	Control (N=)	A&T (N=)	Control (N=)		
	Percent/Mean (SD)	Percent/Mean (SD)	Percent/Mean (SD)	Percent/Mean (SD)		
Dietary diversity score						
Consumption of unhealthy foods						
Meal frequency						

Controlling for clusters by school only.

Adjusted for AG age, household food security and wealth tertile, and clustered by school.

\*\*\* p<0.01; \*\* p<0.05; \* p<0.1

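### The adjusted impact model includes household food security, which for at least 70% of girls can only be an endline value, and the SAP does not say whether the adjusted or the unadjusted estimate is primary

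*SAP*

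**What the plan says.** SAP 3.3 bases the main analysis on the endline survey: "Given that the main impact indicators with full sample sizes were collected at endline only, linear regression models will be used" to compare the arms, with standard errors clustered by school. Table 6 then has two columns of results. The unadjusted column accounts only for clustering. The adjusted column is "Adjusted for AG age, household food security and wealth tertile, and clustered by school". The text above the table gives a different rule for choosing covariates: "we will control for covariates such as adolescent girl age and other variables that differed between study arms". Neither place says from which survey round the covariates come, and the SAP does not say which column decides the primary result.

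SAP 1.2 describes the two surveys as "thereby creating panel data at the school level (not at individual level"). Protocol 2.6 explains that the first round was small: "At baseline, a light data collection at schools and subsamples of adolescent girls and their parents will be conducted". Its Table 3 gives 81 girls and 81 parents per arm at baseline. For the second round, "The sample size at endline will be rounded to 270 girls per group", and the same section says that this sample takes in girls already surveyed at baseline.

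Food security is measured by interview with the HFIAS, in both the parent questionnaire (Protocol 4.1.5, module 11) and the girl questionnaire (Protocol 4.1.4, module 11). The SAP does not say which respondent's answers enter the model.

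Protocol 2.3, Table 2, lists three activities aimed at intervention-arm parents: parent-teacher meetings on nutrition, community gatherings, and "Home visits by HEWs and/or community volunteers to discuss with parents about adolescent nutrition, dietary diversity" and related topics. Protocol 3.2 states that the study is unblinded.

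**The concern.** Randomisation makes the arms comparable in everything fixed before the intervention starts. It gives no such protection once the analysis conditions on something recorded afterwards that the intervention may have altered. Food security at endline could be altered in two ways. Households might manage food differently after the parent activities, or parents and girls who have heard messages about diet might answer the same questions differently.

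In either case, holding food security constant takes out the part of the programme's effect that runs through it. If some unmeasured factor drives both food security and diet, it also adds bias. The adjusted figure would then answer a different question from the one the trial was designed for. Because neither column is named as primary, that figure could become the headline result.

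The covariate rule in the text could make this worse. SAP 3.2 compares characteristics between arms at both rounds. If differences seen at endline count, the rule would tend to select the very variables that the intervention had moved.

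**Working it through.** **Step 1. Which round can the covariate come from?** Inputs: 81 households per arm at baseline and 270 at endline, from 27 schools per arm (Protocol 2.6; SAP 1.3).

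- Largest possible share of endline girls with their own baseline value: 81 / 270 = 30%. This needs every baseline girl to be found again, still eligible, and linked.
- Smallest share that can only have an endline value: (270 − 81) / 270 = 70%.
- Baseline households per school: 81 / 27 = 3.

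Endline timing is therefore an inference from the design, but a firm one for at least 70% of girls.

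**Step 2. What would adjustment do?** Let food security have SD 1 within arms, with higher values meaning more secure. Define:

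- a = effect of the programme on measured food security, in SD;
- b = food groups per SD of food security;
- g = food groups per SD of an unmeasured common cause of food security and diet;
- u = correlation of that cause with food security within arms.

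In a linear model, unadjusted estimate − adjusted estimate = a × (b + g × u).

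The documents give none of these four quantities, so the table is an illustration on assumed values. It takes a true total effect of 0.5 food groups (the SAP 1.3 target) and shows the expected adjusted estimate, 0.5 − a × (b + g × u). The common cause, where present, has g = 0.5 and u = 0.5, so g × u = 0.25.

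| a | b = 0.2, no common cause | b = 0.6, no common cause | b = 0.2, common cause | b = 0.6, common cause |
|---|---|---|---|---|
| −0.3 | 0.56 | 0.68 | 0.635 | 0.755 |
| −0.1 | 0.52 | 0.56 | 0.545 | 0.585 |
| 0 | 0.50 | 0.50 | 0.50 | 0.50 |
| 0.1 | 0.48 | 0.44 | 0.455 | 0.415 |
| 0.3 | 0.44 | 0.32 | 0.365 | 0.245 |

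The unadjusted estimate has expectation 0.5 in every cell. For a = 0 to 0.3, a simulation of 54 schools with 10 girls each (SD 1.56 and ICC 0.015, both from Protocol 2.6; 600 replicates per scenario) gave differences within 0.005 food groups of the formula. The rows with negative a follow from the formula alone.

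**Step 3. Reading the table.** If a = 0, nothing happens. If a is positive, the adjusted estimate is too small as a measure of the total effect. If a is negative, for example because messages about diet make respondents report more insecurity, it is too large. With a common cause, the adjusted estimate also misses the direct effect (total − a × b). At a = 0.3 and b = 0.6 the direct effect is 0.5 − 0.18 = 0.32, while the adjusted estimate is 0.245.

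**The case against.** The strongest reply is that nothing in the documents shows the programme acting on food security. Protocol Table 2 lists education, mentoring, BMI counselling, meetings, training and supervision, with no food, cash or vouchers. Delivery lasted about four months (SAP 1.2). Among the activities aimed at parents, the SAP counts only the parent-teacher meetings as core. SAP 3.2 treats food security as a household characteristic, and the RQ3 indicator tables do not list it. What they do list is the availability of food groups at home, which is a different measure. On this view a is close to zero and adjustment does no harm. This stands as a limit on size: zero is a credible value. It does not show that a is zero. The scale is self-reported, the trial is unblinded, and both questionnaires carry a social-desirability module, so the study team already regards response bias as worth measuring. In partial mitigation, Protocol 3.2 says that girls in intervention areas will not be told the result of the randomisation.

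A second reply is that the plan has safeguards: the unadjusted column would expose any shift, and a difference-in-differences robustness test is planned. This also stands. It limits the point to the adjusted column, but does not tell the reader which column to believe if they disagree.

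A reader might go further and infer from the table that adjustment would hide 4% to 36% of the effect (0.02 / 0.5 to 0.18 / 0.5). The documents do not support that. The range uses assumed inputs, leaves out a = 0, and takes for granted that the shift is downward.

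**Conclusion.** The point holds in limited form. The adjusted model conditions on a variable that, for at least 70% of girls, can only have been recorded after the intervention, and that the intervention could have changed in fact or in the reporting. If it did, the adjusted estimate does not target the total effect of the programme. Size and sign cannot be determined from the documents, and zero is possible.

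It should not be read as saying that the trial's result is biased, or that food security is known to lie on the causal path. The unadjusted comparison keeps the full protection of randomisation. The weakness is that the SAP leaves open which estimate is primary, while one of the two candidates carries this avoidable risk. The conclusion rests on the endline timing inferred in Step 1; the survey round is not stated.

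**What to change.** In SAP 3.3 and footnote 2 to Table 6:

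- Name the primary estimate in advance.
- Limit its covariates to those the intervention cannot affect: woreda, girl's age and grade. Woreda is the randomisation stratum (Protocol 3.1) and is missing from the footnote. Replace the rule about variables that differ between arms with this fixed list, so that text and footnote agree.
- Treat the school's baseline mean dietary diversity as optional. It rests on about 3 girls per school from before the COVID-19 interruption, so it is noisy.
- Report the model with endline food security only as a labelled sensitivity or pathway (RQ3) analysis, stating the round and the respondent. Wealth tertile is also an endline value for most girls. It is less likely to change in about four months, but if it stays in the primary model the SAP should say why.

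The cost is a change of SAP wording and six woreda terms (7 − 1) with 54 schools. Some precision may be lost if endline food security strongly predicts diet.

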#### 3.3.1 Analysis of program impact pathways [RQ3]

In addition to the estimation of impacts, we will conduct plausibility analysis to provide further evidence for the likelihood or strength of our impact estimates, by examining the intermediate outcome indicators along the program impact pathways (from service delivery to exposure and behavioral

determinants) to determine whether the program resulted to the outcomes as intended by design. The program impact pathway (PIP) was developed in collaboration with the A&T program team to map out the mechanisms through which the interventions were expected to achieve impact. The purpose of the PIP analysis is to lay out the theoretical causal links between program activities, outcomes, and impacts. We will examine key indicators along the components of pathways (presented in RQ3), to interpret and support the impact evaluation results. We will compare differences between program groups for indicators along the pathway matched to the relevant outcomes, using linear regression models accounting for school clustering.

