### 4.4 Statistical methods

Data analysis will use econometric analysis to control for (any) differences at baseline and between intervention and comparison groups for all relevant variables of interest. Statistical testing for differences between the two groups will be done using a random effects regression, accounting for the clustering of errors within and across schools.

The randomized study design allows for the identification of causal effects of the adolescent nutrition intervention through comparisons of mean outcomes between the treatment and control groups. Key indicators will include dietary diversity. Impact will be assessed using “difference-in-difference” (DID) estimation and/or analysis of covariance (ANCOVA) controlling for covariates. Data management, data cleaning and statistical analyses will be conducted using Stata version 16 (Statacorp, USA). The statistical significance for tests will be set at 5% for main effects or 10% in case of interactions. All statistical tests will be one-sided.

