### III. Statistical Analysis Plan

#### 3.1 General principles and methods

Data analyses will be performed using STATA version 17.0 (StataCorp LLC). All applicable statistical tests will be two-sided to allow potential findings of unexpected effects. Statistical significance will be presented at levels of  $p<0.05$ ,  $p<0.01$ , and  $p<0.001$ .

A diagram presenting the flow of clusters and individuals through the trial, based on the Consolidation Standard of Reporting Trials (CONSORT) statement: extension to cluster randomized trials (1,2), is shown as follows.

[figure not shown]

Figure 1. CONSORT flow diagram for repeated cross-sectional surveys

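### The pathway comparisons of schools, principals, teachers and health extension workers name no baseline term, although both rounds cover the same 54 schools; ANCOVA would also be a sharper robustness check than difference-in-differences

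*SAP*

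**What the plan says.** SAP 1.2 describes repeated cross-sectional surveys in the same 54 schools, "thereby creating panel data at the school level" but not at the level of individuals. SAP Table 1 gives 27 per arm for principals, science teachers, HEWs and school checklists at baseline and again at endline. Girls and parents number 81 per arm at baseline and 270 per arm at endline. Protocol Table 3 has the same figures for people, and Protocol 4.1 lists one set of tools for both surveys.

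SAP 3.3 bases the main impact model on endline data and gives the reason: "Given that the main impact indicators with full sample sizes were collected at endline only". The adjusted model in Table 6 uses girl's age, household food security and wealth tertile. Baseline outcomes enter only through a difference-in-differences (DID) robustness test, where the outcome exists at baseline.

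SAP 3.3.1 compares the arms on the pathway indicators of Table 4 "using linear regression models accounting for school clustering" and says nothing about baseline. Protocol 4.4 had promised control for baseline differences, by DID and/or "analysis of covariance (ANCOVA) controlling for covariates".

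**The concern.** The pathway analysis is meant to show whether the impact estimates are plausible, by following the chain from service delivery to behaviour. For staff and school indicators it rests on 27 schools per arm, so only large differences can be detected and a chance imbalance at baseline can pass for an effect or hide one. The same school's value from 2019 is planned for every school. Where that value predicts the 2021 value, conditioning on it removes between-school noise and chance imbalance without new data. The section on these models does not say whether it will be used.

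A second issue sits in SAP 3.3. The only planned analysis of girls' diets that uses baseline outcomes is DID, which carries the full sampling error of a small baseline sample into the estimate. A check with a much larger standard error than the main analysis can neither support nor contradict it.

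**Working it through.** **Inputs.** From Protocol 2.6: alpha 0.05; power 80%; SD 1.40 and ICC 0.18 for the original calculation; SD 1.56 and ICC 0.015 for the later one; 270 girls per arm as 10 in each of 27 schools. From Table 3: 81 baseline girls per arm. Assumed, because the documents do not give them: three baseline girls per school (81/27, evenly spread); the baseline-endline correlation r of a school's staff or checklist value; and the correlation CAC of true school means between rounds. The sum of normal quantiles is 1.960 + 0.842 = 2.802, two-sided. The SAP says "All applicable statistical tests will be two-sided" and the protocol "All statistical tests will be one-sided"; only the two-sided version reproduces the stated sample size.

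**The plan's own figures.**
- Unclustered n = 2 × (1.40 × 2.802 / 0.6)² = 85.5 per arm. With 27 schools fixed, girls per school = 85.5 × 0.82 / (27 − 85.5 × 0.18) = 6.03, rounded up to 7, and 7 × 27 = 189. This matches the protocol exactly. One-sided gives 4 × 27 = 108.
- For 270 per arm, SD 1.56 and ICC 0.015, the design effect is 1 + 9 × 0.015 = 1.135. SE = 1.56 × √(2 × 1.135 / 270) = 0.143, and the detectable difference is 2.802 × 0.143 = 0.40. The protocol states 0.5, which is conservative for those inputs.

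**Staff and checklist indicators, one value per school.** Endline only: 2.802 × √(2/27) = 0.76 SD (0.77 with a t quantile). With the baseline value as covariate, variance is multiplied by (1 − r²) × 1.02, where 1.02 is the approximate cost of estimating one slope on 54 schools.

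| Assumed r | Variance factor | Simulated variance ratio | Detectable difference (SD) |
|---|---|---|---|
| 0.1 | 1.010 | 1.01 | 0.77 |
| 0.3 | 0.928 | 0.93 | 0.73 |
| 0.5 | 0.765 | 0.77 | 0.67 |
| 0.7 | 0.520 | 0.51 | 0.55 |

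At r = 0.5 the gain equals having 27 / 0.765, or about 35, schools per arm.

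**Girls' dietary diversity, school baseline mean as covariate.** r² = CAC² × [3·ICC / (1 + 2·ICC)] × [10·ICC / (1 + 9·ICC)].
- ICC 0.015, CAC = 1 (the most favourable case): r² = 0.0437 × 0.1322 = 0.006. The detectable difference is 0.401 without the covariate and 0.404 with it, after the slope cost. Simulated variance ratio 1.01 to 1.02. No gain.
- ICC 0.18, CAC 0.5 to 1: variance ratio 0.95 to 0.76 (simulated); detectable difference 0.61 falling to between 0.59 and 0.52.

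**Girls' dietary diversity, DID.** SE² = 2 × [σ²(1 + 9·ICC)/270 + σ²(1 + 2·ICC)/81 − 2·CAC·ICC·σ²/27], with σ = 1.56.
- ICC 0.015, CAC 0.5: 2 × (0.01023 + 0.03095 − 0.00135) = 0.0796, so SE = 0.282, which is 1.97 times 0.143. At CAC 0.9 the ratio is 1.95. The detectable difference is about 0.78 to 0.79 food groups, against 0.40 endline-only.
- ICC 0.18: endline-only SE is 0.217; the DID ratio is 1.43 at CAC 0.5 and 1.22 at CAC 0.9.

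The DID formula treats the girls in the two rounds as different individuals, as the SAP does. Protocol 2.6 says the endline will include those surveyed at baseline; any such overlap would make the DID SE somewhat smaller than shown.

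**The case against.** The case against has several sound parts. The correlation r is unknown, and for many Table 4 indicators it may be low. Training on adolescent nutrition, BMI measurement and mentoring may be close to zero everywhere at baseline. The respondent may also have changed between 2019 and 2021, since the link is by school and not by person. Table 1 counts respondents and does not show that every indicator was measured the same way twice; Protocol 2.6 calls the baseline a light data collection, and its timeline schedules separate development of the endline tools. RQ3 outcomes are secondary, the study was not sized on them, and the unadjusted randomised comparison is unbiased. All of this stands. It limits the fix to suitable indicators but does not remove the reason for it.

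A reader might infer more than the documents support, in four ways:
- *That the main endline model wastes precision.* At the protocol's current ICC of 0.015 it does not. A worthwhile gain needs an ICC nearer the earlier 0.18, which was paired with an external survey and a 9-group score.
- *That the SAP gives a false reason for omitting baseline from the pathway models.* The reason about full samples is in 3.3 and concerns the main impact indicators. Section 3.3.1 does not invoke it; it is simply silent.
- *That the SAP broke a commitment by dropping ANCOVA.* The protocol wrote DID and/or ANCOVA, and the SAP keeps DID. The protocol also does not say that the ANCOVA covariate would be the school's baseline outcome.
- *That adjustment costs nothing.* At r near 0.1 it raises variance by about 1%.

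**Conclusion.** The point holds for the staff and checklist indicators in SAP 3.3.1, as an unspecified model that leaves usable baseline data without a stated role. The size depends on r: variance falls by about 7% at 0.3, 23% at 0.5 and 49% at 0.7, with nothing gained near 0.1. The calculation assumes one value per school. Table 4 groups principals and teachers, so some indicators may have two values per school, which would change the starting figure of 0.76 SD.

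For girls' diets, the endline-only primary model is a sound choice and should stay. The weak part is the robustness check: under the stated assumptions DID has about 1.2 to nearly 2 times the standard error of the model it is meant to test. ANCOVA on the same data is at worst about 1 to 2% worse in variance than the endline-only model. The matter is worth correcting but does not threaten the primary result.

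**What to change.** In SAP 3.3.1:
- State that arms are compared at endline.
- Pre-specify the same school's baseline value as a covariate for checklist, principal, teacher and HEW indicators that were measured the same way in both rounds and were not near zero at baseline. Knowledge scores, infrastructure and checklist items on the food environment are likely candidates.
- List those indicators in the SAP, chosen from baseline data pooled over arms and before any endline comparison. Leave the rest unadjusted.

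In SAP 3.3:
- Keep the endline-only model as primary.
- Make ANCOVA on the school's baseline mean of the outcome the baseline-adjusted robustness analysis, instead of DID or alongside it. If DID stays, report it with a note on its expected precision.
- Reconcile Protocol 2.6, on re-surveying the baseline girls, with the SAP's statement that there is no individual panel.

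The cost is SAP wording and one degree of freedom per model, with a small loss of precision where the correlation turns out near zero. No new data are needed.
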